## 1.2 Investigational Agent

[figure not shown]
SPP1 is a pro-inflammatory inducer of skin fibrosis and aging. Screening pharmaceutically active compounds that inhibit the SPP1 promoter led to the discovery of pentamidine isethionate, which inhibited SPP1 promoter activity by  $\geq 80\%$  with minimal in vitro cell toxicity. Mayo Clinic Compounding Pharmacy was utilized to produce pentamidine isethionate, delivered as topical cream formulation containing 2% TP in PCCA PP base.

## 1.3 Preclinical Data

Pre-clinical testing (animal and biocompatibility) of TP in silicone base (PCCA PP) demonstrated safety and biocompatibility across numerous rabbit models of hypertrophic scar formation. Pre-clinical animal and biocompatibility data are provided below.

[figure not shown]
We developed a hypertrophic scar formation rabbit ear model following IACUC approval (A00001970-16). Surgical ligation of leporine auricular vessels induced an ischemic landscape for hypertrophic scar production. Specifically, cranial artery and vein were ligated; caudal artery and vein were preserved; and central artery was ligated but central vein was preserved in the rabbit ear (Figure 1A). Following vascular ligation, one linear full-thickness skin wound was created on the ventral side of each ear with a surgical blade. The skin and perichondrium were removed and wound edges were closed with 4-0 Nylon sutures, generating tension for hypertrophic scarring.

Following ischemic wounding, we assessed the relative ischemia created in the ear at time of surgery and time of sacrifice with a fluorescent light assisted angiography (Spy Elite, LifeCell) (Figure 1B). Ischemic perfusion coupled with mechanical suture tension yielded hypertrophic scar formation.

**Figure 1. Ischemic Rabbit Ear for Hypertrophic Scar Model.** Surgical Ligation of Leporine Auricular Blood Vessels, A. Fluorescent light-assisted angiography (Spy Elite) with and without Doppler, B.

Following vascular ligation and linear wounding, rabbits were assigned to treatment groups: (1) control group with synthetic bandage (no treatment), (2) PCCA PP (base only), or (3) TP in PCCA PP. Treatment with 2% TP in PCCA PP demonstrated scar reduction following 4 weeks of topical gel application (Figure 2). These results provide proof-of-concept for the proposed trial using 2% TP in PCCA PP for hypertrophic scar reduction.

**Figure 2. Hypertrophic Scar Reduction.**

#### 1.4 Clinical Data to Date

There is no available clinical research data to date on topical application of pentamidine isethionate to treat hypertrophic scarring.

## 1.5 Dose Rationale

Drug titration testing with 1%, 2% and 5% pentamidine isethionate identified 2% as the optimal active dose for wound healing.

## 1.6 Study Risks and Benefits

### 1.6.1 Anticipated Risks

Although the risk is extremely small, subjects are theoretically at increased risk of infection through participation in this study. In addition to standard of care with surgical scar excision (SSE), patients in this study will have skin biopsied from their scar site. There also exists a potential risk for adverse skin reactions following topical drug application and/or concomitant drug interactions. The type of infections and adverse skin reactions that are theoretically possible and how we will monitor and address are listed below:

- Acute soft tissue infection:

Risk of infection from scar excision alone is extremely low. In [name] practice, there has been very limited instance of infection. However, we will contact patients by phone at 24 hours post-discharge as well as at 2 months and 3 months to address any of the following symptoms: increasing pain at the wound site, redness around the wound or fever [defined as body temperature above 100.4°F (38.0°C)], as deemed appropriate by the primary investigator. In addition, the study subjects will be asked to self-monitor for symptoms of pain or fever and contact the study investigators immediately if they have any of above symptoms.

- Adverse skin reactions:

In its use as an antifungal treatment, topical pentamidine (TP) has been proven to have minimal to no adverse skin reactions (Patent Publication# US5230897-A). We will be monitoring patients weekly during the first month. Follow-up visits at week 2 and week 4 will assess change in physical exam or pattern of pain. Patients will also be encouraged to self-monitor for symptoms of pain or fever. Patients will seek immediate medical attention for fever above 103°F (39.4°C).

With the proposed protocol, acute risks exist and are as follows:

- Pain
- Itching
- Urticaria
- Infection
- Inflammation
- Bruising
- Crusting/Scabbing
- Hyper/hypo/depigmentation
- Thickening of the skin
- Change in vascularization

### **1.6.2 Overall Study Risk Management**

The following measures implemented by Mayo Clinic will minimize the risks associated with patients' participation in the clinical study:

- Mayo Clinic selects personnel with extensive experience in conducting clinical studies and in performing procedures involved in the protocol including skin biopsies and surgical procedures.
- All examinations, treatment procedures and interpretation of clinical data generated during the study is directed, overseen and analyzed by an appropriately licensed and credentialed physician who has been trained to the clinical study protocol.
- Mayo Clinic developed the clinical protocol and training programs to ensure that the study personnel at Mayo Clinic have a strong knowledge and understanding of the clinical protocol, including patient selection criteria and procedure requirements.
- Mayo Clinic carefully developed patient eligibility criteria for the investigation including clearly defined inclusion and exclusion criteria to ensure that only properly selected patients will be enrolled in the clinical study.
- The protocol is designed so that patient treatment and follow-up procedures will be consistent with those of the clinically established standard of care.

### **1.6.3 Scar Excision and Skin Biopsy Risk Management**

Investigators and all study personnel will be trained in the details of all aspects of the study procedures. To minimize risks and increase the chances of a favorable clinical outcome the following measures are required:

- Enrollment of subjects who qualify per the inclusion/exclusion criteria in the protocol
- Strict adherence to the study protocol
- Use sterile technique throughout the procedure
- Use standard of care for the monitoring of and treatment of possible adverse events following scar excision and biopsy procedure
- Depending on the site of the scar, the surgeon will explain the types of activities to avoid
- Close surgical incision and biopsy site with appropriate suture

### **1.6.4 Adverse Reaction Risk Management**

Investigators and all study personnel will be trained in the details of all aspects of the study procedures. Standardization of topical drug and placebo application techniques is critical to a good clinical outcome. To minimize risks and increase the chances of a favorable clinical outcome the following measures are required:

- Subjects will be educated on treatment application during pre-operative visit
- Potential risks will be listed in the patient consent form and quantified during the course of treatment via patient questionnaires (VSS and POSAS)
- Follow-up will continue for 3 months following surgery: in-person appointments with study staff will occur during treatment period at 2 weeks and 4 weeks after surgery. A final visit will be encouraged at 3 months after surgery. A follow-up phone call will be made by study staff 24 hours after surgery and postoperative weeks 1 and 3, and month 2 (and 3 if the patient is unable to return for in-clinic follow-up).

### 1.6.5 Potential Benefits

Each patient will receive both treatment and within subject placebo following SSE. Either the distal or proximal portion of the wound will receive the investigative treatment (TP) versus placebo (PCCA PP) with adjuvant SSE. Our preclinical data suggests that topical treatment with pentamidine may provide an improved environment for lesion healing in the setting of hypertrophic scar. However, this has not been formally tested for safety or efficacy in a RCT within the United States. As far as cosmetic benefits, patients will have the potential for the reduction of visible scarring. Hypertrophic scarring can cause patients to experience physical pain, as well as psychological and social costs that can be emotionally and financially difficult. The proposed topical treatment aims to reduce the thickness, redness and altered pigmentation of scar tissue by targeting the root cause of pathological scarring and fibrosis. Thus, the focus of this pilot study will be procedural safety and preliminary efficacy.

## 2 Study Objectives

The primary goal of this randomized clinical trial will be to directly evaluate safety of topical scar prevention product and placebo base control in patients with hypertrophic scarring. Patients with known diagnosis of hypertrophic scar will be enrolled. Secondarily, we will evaluate initial signs of treatment efficacy using topical product.

## 3 Study Design

### 3.1 General Description

This study is a double-blind pilot study of scar excision procedure followed by treatment with either TP in PCCA PP versus PCCA PP silicone base only. Current management for patients with hypertrophic scar includes silicone-based treatment. At our institution we treat patients with scar excision surgery without topical scar cream following the procedure. However, a significant proportion of patients continue to fail this treatment modality leading to scar recurrence. Indeed, individual patient response to therapy varies based on patient characteristics including ethnicity. As such, we plan to treat the same patient with both TP in PCCA PP and PCCA PP alone at different ends of their scar. In this way, we can better determine efficacy of these topical agents in biologically controlled setting with reduced response variability. We plan to enroll patients with minimum hypertrophic scar length  $\geq 3$  cm.

Those patients who successfully qualify based on inclusion and exclusion criteria will be invited to participate in the trial. Following informed consent, eligible subjects will undergo pre-operative tests to include blood work and EKG. Preoperative photographs of the scar site will be taken. Scar quality questionnaires (VSS and POSAS) will be completed and a scar ultrasound performed.. A 5-mm skin punch biopsy will be obtained from the lateral edge of the scar at both the proximal and distal ends of the scars, under local anesthesia. Alternatively, the first punch biopsy may occur prior to the surgical procedure while the patient is under anesthesia. Part of the sample will be stored in formalin and prepared for histological staining. The other portion will be frozen and prepared for molecular analysis. All participants will receive both treatments to be applied either at the proximal end or the distal end of the scar. Treatment application will be randomized. For example, topical agent A will be applied to the proximal end of the scar and will contain either TP

in PCCA PP or PCCA PP. Topical agent B will treat the distal portion of the scar and contain either TP in PCCA PP or PCCA PP alone. 1-2cm in the middle of the scar will remain untreated as the border zone. It is known that blood perfusion influences scar formation; thus to reduce potential bias from distal scar site receiving reduced blood flow compared to proximal scar site, treatment application will be randomized to scar site. Prior to treatment initiation, patients will undergo scar excision procedure with a 24-hour recovery period. Treatments will be provided in single dose containers for application every 48 hours following surgical recovery (total of 14-16 applications; total treatment duration of 4 weeks).

## Patient Treatment Schema

### Visit 0: (Preoperative screening)

- Informed consent

### Visit 1: (Preoperative period)

- Pre-operative evaluation including history, clinical exam with baseline neuropsychiatric assessment, and laboratory studies to include hepatic and renal function, complete blood count with differential, blood glucose level and calcium. The specific laboratory tests for hepatic and renal function will include ALT, AST, Bilirubin, BUN and Creatinine. Any abnormal value twice the upper limit of normal will meet exclusion criteria: AST (Normal: 8-48 U/L); ALT (Normal: 7-55 U/L); Bilirubin, Total (Normal <= 1.2 mg/dL); BUN (Normal 8-24 mg/dL); Creatinine (0.8-1.3 mg/dL).
- Baseline cardiac monitoring (ECG)
- Scar photography
- Quality questionnaires (VSS and POSAS)
- Pre-operative US and/or 3D imaging
- Treatment application patient education
- 5-mm skin punch biopsy under local anesthesia from distal and proximal sites (Alternatively, the first punch biopsy may occur prior to the surgical procedure while under anesthesia.)

### Visit 2: (Day of procedure)

- Surgical scar excision under local or general anesthesia depending on size of scarring and surgeon preference for excision
- Provide single dose containers with de-identified treatment agents (TP in PCCA PP and PCCA PP alone) and treatment recording log for two weeks

### Phone Interview #1: (Week 0, Day 1 postop)

- Assessment of adverse events

### Phone Interview #2 (Week 1 postop)

- Assessment of adverse events

### Visit3: (Week 2 postop)

- Scar photography
- Quality questionnaires (VSS and POSAS)

- Post-operative evaluation including clinical exam with local safety evaluation to assess tolerability (e.g. erythema, edema, vesicle formation, necrosis, ulceration etc.) and neuropsychiatric adverse event assessment
- Laboratory studies (including hepatic and renal function, complete blood count with differential, blood glucose level and calcium)
- Post-operative cardiac monitoring (ECG)
- Post-operative US and/or 3D imaging
- Provide single dose containers with de-identified treatment agents (TP in PCCA PP and PCCA PP alone) and treatment recording log for two weeks

**Phone Interview #3 (Week 3 postop)**

- Assessment of adverse events

**Visit4: (Week 4 postop)**

- Scar photography
- Quality questionnaires (VSS and POSAS)
- Post-operative evaluation including clinical exam with local skin reaction evaluation and neuropsychiatric adverse event assessment
- Laboratory studies will include hepatic and renal function, complete blood count with differential, blood glucose level and calcium. Post-operative US and/or 3D imaging
- 5-mm skin punch biopsy under local anesthesia from distal and proximal sites

**Phone Interview #4: (Month 2 postop)**

- Assessment of adverse events

**Visit #5: (Month 3 postop)**

[figure not shown]
- Scar photography
- Quality questionnaires (VSS and POSAS)
- Assessment of adverse events
- Note: if the patient is unable to return for an in-clinic appointment, a phone interview will be conducted

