**Study Summary**

Title	Double Blind, Single-Center, Randomized, Within-Subject Placebo, Phase I Study Evaluating the Effects of Topical Pentamidine in Prevention of Hypertrophic Scar Formation
Running Title	Novel Topical Gel for Hypertrophic Scar Prevention
IRB Protocol Number	17-005230
Phase	Pilot Study
Methodology	Double Blind, Single-Center, Randomized, Within-Subject Placebo Phase I Study
Overall Study Duration	3 months
Subject Participation Duration	3 months
Single or Multi-Site	Single site
Objectives	Evaluate safety of topical pentamidine (TP) as an adjuvant to surgical scar excision (SSE) in the treatment of hypertrophic scar formation. Safety will be measured by serial monitoring for adverse events following the procedure and during treatment duration. Secondarily, study will evaluate drug quality and standardizations as well as investigate initial signs of efficacy.
Number of Subjects	10
Diagnosis and Main Inclusion Criteria	Hypertrophic scar diagnosed in Mayo Clinic Department of Dermatology or Division of Plastic Surgery, Rochester, Minnesota.
Study Product, Dose, Route, Regimen	Pentamidine, delivered as topical formulation containing 2% TP in silicone-containing base, PCCA Pracasil™-Plus (PP), versus placebo base alone. Approximately 1.8 mL of product in allotted single dose containers will be applied every 48 hours for 4 weeks following surgical scar excision.
Duration of Administration	Once every 48 hours for 4 weeks.
Reference therapy	SSE with silicone compounding base only (PCCA PP).
Statistical Methodology	The primary analysis will use descriptive statistics to document adverse events between treated and untreated lesions. The secondary analysis will use paired t-test or Wilcoxon signed rank test to compare the change in lesion height and characteristics between the treated and placebo groups following SSE (TP + PCCA PP vs. PCCA PP alone). In addition, two-factor analysis of variance (ANOVA) with repeated measures on both factors will be used to evaluate the effect of treatment and follow-up time for other continuous measures such as Vancouver Scar Scale (VSS) and Patient and Observer Scar Assessment Scale (POSAS).

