#### 4.3 Subject Recruitment, Enrollment and Screening

Prior to discussing study enrollment with the patient, principal investigator, [name] and/or [name], will discuss with study coordinator to ensure that that target enrollment has not yet been met.. Subjects will be recruited at Mayo Clinic Department of Dermatology and Division of Plastic Surgery in Rochester, Minnesota.

At the time of patient enrollment in the trial the following must be verified:

1. IRB approval of the trial and open enrollment status with both Mayo Clinic and clinicaltrials.gov.
2. Open place on the enrollment log (confirmation from the PI and study coordinator).
3. Patient is willing and able to travel to the Mayo Clinic, Rochester for all tests, treatment and follow up required in the protocol.

At the time of patient enrollment the following will be confirmed and documented:

1. A signed consent form.

2. The existence of a signed authorization for use and disclosure of protected health information.
3. A completed inclusion/exclusion enrollment checklist.

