## **6.9 Phone Interview #4: (Month 2 post op)**

Patients will be contacted 2 months following scar excision. Any adverse effects present will be assessed and noted. Measures to address these effects will be taken on a per-patient basis.

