## **6.10 Visit #5: (Month 3 post op)**

The scar will be photographed and quality questionnaires (VSS and POSAS) will be completed. Patients will be assessed for any adverse events.

Range for phone interviews for call 2 and 3: +/- 1 day

Range for phone interview for call 4: +/- 1 week

Range for study visits 3 and 4: +/- 1-3 days

Range for study visit 5: +/- 2 weeks

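### Month 3 can become a phone call of undefined content, which puts at risk the only VSS, POSAS and photographs from the treatment-free follow-up and, through the analysis rules, possibly the patient's other data

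*Combined protocol and SAP*

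**What the plan says.** Section 6.10 makes Month 3 a data-collecting visit: "The scar will be photographed and quality questionnaires (VSS and POSAS) will be completed". The schedule of events (section 6.11) marks Visit 5 for photography, both scales and adverse events. Section 3.3 counts it among the five visits. None of the three mentions a phone alternative.

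Two other places do. The schema in section 3.1 lists the same assessments and then adds "Note: if the patient is unable to return for an in-clinic appointment, a phone interview will be conducted". Section 1.6.4 says "A final visit will be encouraged at 3 months after surgery" and extends the list of calls to Month 3 with "and 3 if the patient is unable to return for in-clinic follow-up". At enrolment, section 4.3 requires this to be verified: "Patient is willing and able to travel to the Mayo Clinic, Rochester for all tests, treatment and follow up required in the protocol".

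The content of the Month 3 call is not defined. For each of the four numbered calls the procedures say "Any adverse effects present will be assessed and noted", and the schedule marks those columns only for the interview and adverse events. Section 1.6.1 describes contact at 2 and 3 months as a check for pain, redness and fever. Section 5.4 adds compliance. No section provides for collecting VSS, POSAS or images remotely.

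On analysis, the Study Summary says that for measures such as VSS and POSAS "two-factor analysis of variance (ANOVA) with repeated measures on both factors will be used to evaluate the effect of treatment and follow-up time". It does not list the time points, and no missing-data method is given. Section 7.3 restricts the analysis to subjects who finished every procedure and all follow-up.

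**The concern.** Ultrasound and biopsy stop at week 4, which section 8.1 treats as the end-of-treatment assessment. Month 3 is therefore the only scheduled efficacy reading from the treatment-free follow-up. It bears on the trial's motivation, since section 3.1 points to scar recurrence after excision. The protocol makes this reading optional in two places and does not say what replaces it.

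The analysis rules can then spread the loss. A permitted substitution at one visit may cost the patient's week-2 and week-4 scores and, on a literal reading of section 7.3, the patient's place in the primary safety summary. The call would have collected safety information that the population rule then discards. The replacement rule in section 4.4.1 covers withdrawals and does not mention a missed Month 3 visit.

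**Working it through.** **The plan's own figure.** Section 7.1 gives 80% power for 1.3 SD with a two-sided unpaired t-test at 0.05. It does not name n; I take 10 per condition from the ten subjects. The noncentrality is d√(n/2) = 1.3 × √5 = 2.91 on 2n − 2 = 18 df. The exact noncentral-t power is 78.5%, and the effect detectable at exactly 80% is 1.325 SD. The stated figure is reproduced to rounding. It is for an unpaired test, whereas the design is within-patient, so the losses below are worked on the paired scale.

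**When treatment ends.** The first application is at 24 hours and then every 48 hours. With 14 applications (section 5.3) the last falls on day 1 + 13 × 2 = 27, before the day-28 visit. Section 3.1 allows 14 to 16. Sixteen would end on day 1 + 15 × 2 = 31, so some patients could still be applying at week 4. The two statements need to be reconciled, but neither makes Month 3 anything other than treatment-free.

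**Cells per patient, for each scale.** The treatment factor requires one score per site, which I take as implied.
- If the pre-operative visit, week 2, week 4 and Month 3 are all levels: 4 visits × 2 sites = 8 cells. Without Month 3 scores, 2 are empty and a conventional fit discards the other 6.
- If only the three postoperative visits are levels: 3 × 2 = 6 cells. Two are empty and 4 are discarded.
- If Month 3 is not a level, no earlier score is lost, but the Month 3 scores have no stated analysis under this model.

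**Error degrees of freedom and power.** With n complete patients, the treatment effect has n − 1 error df, and the time effect with four occasions has 3(n − 1). With two treatments, the complete-case treatment test is equivalent to a paired t-test on each patient's visit-averaged difference, with noncentrality δ√n, where δ is the difference in SDs of that within-patient difference (two-sided 0.05).

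| Complete patients | Treatment error df | Time error df | δ detectable at 80% power | Power for δ = 0.996 |
|---|---|---|---|---|
| 10 | 9 | 27 | 0.996 | 80.0% |
| 9 | 8 | 24 | 1.067 | 74.5% |
| 8 | 7 | 21 | 1.156 | 67.8% |
| 7 | 6 | 18 | 1.273 | 59.7% |

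**How likely a loss is.** The documents give no rate for the phone option. If each patient uses it independently with probability q, the chance that at least one of ten does is 1 − (1 − q)^10. This is 40% for q = 5%, 65% for 10%, 89% for 20% and 97% for 30%. Expected complete patients are 9.5, 9, 8 and 7.

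**The case against.** The strongest reply is that the fallback helps. A patient who cannot return has no clinic data with or without a call, and the call secures safety information, which is the primary objective. That stands: the option should stay, with its content defined.

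Three stronger readings are tempting, and the documents do not support them.

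- A reader might infer that a phone Month 3 certainly yields no VSS or POSAS. The documents do not say so. The note in section 3.1 sits under a list that includes both scales and does not withdraw them. Sections 1.6.4 and 3.5 treat the scales as patient questionnaires or patient-reported measures. Only clinic photographs and in-person observer ratings are clearly out of reach. The absence of scores is a probable consequence, inferred from how the other calls are described.
- A reader might call Month 3 the only efficacy reading after treatment. Sections 6.8 and 8.1 describe week 4 as post-treatment, and it carries photographs, both scales, imaging and biopsy. Month 3 is unique only as follow-up during the treatment-free period.
- A reader might see a direct contradiction with section 4.3. That criterion covers follow-up the protocol requires, and a visit that is only encouraged need not be required. This is a tension that also makes non-attendance less likely, as does the two-week window either side of Visit 5.

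It is also fair that these are secondary endpoints in a ten-patient pilot. Both sites of a patient are lost together, so the within-patient balance survives. Selection would bias the treatment comparison only if attendance is related to the difference between sites, which is possible but cannot be shown from the documents.

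**Conclusion.** The point holds as a gap with avoidable consequences. The Month 3 sections disagree on whether a phone call may replace the visit, and where they allow it they do not say what it collects. A patient using the option would probably lack Month 3 scale scores and would lack clinic photographs and observer ratings.

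Further loss is conditional. Earlier VSS and POSAS scores drop out if Month 3 is an ANOVA level and the fit is a conventional complete-case one. Removal from every analysis, including safety, follows from section 7.3 only if the call does not count as completed follow-up.

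On the assumption that 1 to 3 of 10 patients are affected, the treatment error df fall from 9 to 8, 7 or 6, and power for a difference set at 80% with ten patients falls to 74.5%, 67.8% or 59.7%. These figures also assume that Month 3 is in the model. The change is worth making because the loss is easily prevented, but it does not invalidate the trial.

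**What to change.** Three changes belong together.

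1. **Month 3 text.** Align sections 1.6.4, 3.1, 6.10 and 6.11 on whether a call may replace the visit. If it may, state that the call also collects the patient part of POSAS, separately for the proximal and distal sites. Keep observer-rated items in person only, say whether VSS is among them, and record the mode of collection. Patient-taken photographs can be optional and supportive only.
2. **Section 7.3.** Replace the completer-only population with all treated subjects for safety, and all subjects with any post-baseline score for VSS and POSAS. Without this, changing the model retains nothing, because the partial records would already have been excluded.
3. **Study Summary and section 7.2.** Replace the complete-case repeated-measures ANOVA with a mixed model containing treatment, visit and their interaction, with patient as a random effect and a term for site within patient, so that repeated scores from one site are not treated as independent. List the visits included and state the missing-at-random assumption.

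The cost is a few minutes on a call already foreseen and a few sentences of text. The downside is that some Month 3 patient scores come by a second mode, and any home photographs are less standard than clinic ones.
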